5 ANALYSIS SETS

In accordance with International Conference on Harmonization (ICH) recommendations in guidelines E3 and E9, the following analysis sets will be used for the analyses.

Safety Analysis Set (SAF) will be used for the analyses of safety variables. Pharmacokinetic Analysis Set (PKAS) will be used for pharmacokinetic analyses. The data from all randomized subjects will be included in the data listings.

The ITT, SAF and PKAS analysis sets will be used for the final end-of-study report.

5.1 Intention to Treatment Set (ITT)

The Intention to Treatment Set (ITT) consists of all subjects who are randomized. The subjects will be analyzed based on the randomized treatments.

The ITT will be used for primary analyses of efficacy data. Selected demographic and baseline characteristics, patient reported outcomes and resource utilization.

5.2 Full Analysis Set (FAS)

The Full Analysis Set (FAS) consists of all randomized subjects with FLT3 mutation based on central test. The subjects will be analyzed based on the randomized treatments.

The selection of subjects for the FAS will be confirmed in the Analysis Set Classification Meeting (ASCM).

The FAS will be used for sensitivity analyses of efficacy data Selected demographic and baseline characteristics will be summarized for the FAS.

5.3 Safety Analysis Set (SAF)

The Safety Analysis Set (SAF) consists of all subjects who received at least one dose of study treatment (ASP2215 or salvage chemotherapy). The subjects will be analyzed based on the actual treatment received.

The SAF will be used for summaries of demographic and baseline characteristics and all safety variables.

5.4 Pharmacokinetics Analysis Set (PKAS)

The Pharmacokinetics Analysis Set (PKAS) consists of the subset of the SAF who received at least one dose of ASP2215 for whom at least 1 plasma concentration datum is available and both the date and time of dosing on the day of PK sampling and the date and time of sampling are known. Additional subjects may be excluded from the PKAS at the discretion of the pharmacokineticist. Any formal definitions for exclusion of subjects or time-points from the PKAS will be documented in the Classification Specifications.

The PKAS is used for all tables and graphical summaries of the PK data.

6 ANALYSIS VARIABLES

6.1 Efficacy Endpoints

There will be no efficacy analysis performed for the end of study report. Summaries of the primary, secondary, and exploratory efficacy results are available in the primary CSR dated 24 JAN 2019 for the data with cutoff date 17 SEP 2018.

6.1.1 Co-Primary Efficacy Endpoint of OS (Second Interim and Final only)

Overall survival (OS) is one of the co-primary efficacy endpoints. OS will be evaluated at the second interim and final analysis. No formal evaluation on OS will be conducted at the first interim. OS is defined as the time from the date of randomization until the date of death from any cause (death date - randomization date + 1). For a subject who is not known to have died by the end of study follow-up, OS is censored at the date of last contact (date of last contact - randomization date + 1).

The date of last contact is the latest date that the subject is known to be alive by the cutoff date. The last contact date will be derived for subjects alive at the analysis cutoff date. Subjects with last contact date beyond the analysis cutoff date will be censored at the analysis cutoff date.

As a sensitivity analysis, OS will be defined similarly as the above primary analysis, however, subjects who undergo an HSCT will be censored at the time of HSCT (HSCT date – randomization date +1).

In addition, as another sensitivity analysis, OS will be defined similarly as the above primary analysis, however, subjects who initiate any new anti-leukemia therapy will be censored at the time of first new anti-leukemia therapy (first new anti-leukemia therapy date – randomization date +1).

During second interim analysis and final analysis, only death events occurring on or prior to the cutoff date are counted as OS events. Subjects with death date after the cutoff date will be censored at the cutoff date.

6.1.2 Co-Primary Efficacy Endpoint of CR/CRh Rate (First Interim only)

The co-primary efficacy endpoint of CR/CRh rate will be evaluated only at the first interim analysis. Complete remission and complete remission with partial hematologic recovery (CR/CRh) rate is defined as the number of subjects who achieve either CR or CRh (as defined in Section 6.1.3.3) at any of the post-baseline visit divided by the number of subjects in the analysis population.

As a sensitivity analysis, CR/CRh rate by cycle 4 will be defined as the number of subjects who achieve CR/CRh by the end of 4 cycles treatment divided by the number of subjects in the analysis population. As another sensitivity analysis, CR/CRh rate prior to HSCT will be defined as the number of subjects who achieve CR/CRh prior to HSCT divided by the number of subjects in the analysis population.

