- c. Includes medications taken within 28 days prior to cycle 1 day 1.
- d. Woman of childbearing potential must have a negative serum or urine pregnancy test (minimum sensitivity 25 IU/L or equivalent units of human chorionic gonadotropin) within 72 hours prior to the start of study treatment.
- e. Screening ECG is required. ECG assessment will be evaluated at predose of cycle 1 day 1, cycle 1 day 8, cycle 1 day 15 and day 1 of each subsequent cycle. Predose assessments should be taken within 1 hour before drug administration. The 12-lead ECGs will be recorded in triplicate (3 separate ECGs 10 minutes resting prior to first ECG and at least 5 minutes apart per time point) and transmitted electronically for central reading. The mean QTcF of the triplicate ECG tracings based on central reading will be used for final treatment decisions and AE reporting. If the mean of the triplicate QTcF is > 500 ms at any time point (by either value on ECG tracing printout or central reading), then triplicate ECGs will be repeated (within 2 hours if based on value on ECG tracing printout and as soon as possible if based on central reading). If the repeat ECG confirms a mean of the triplicate QTcF > 500 ms, dosing of ASP2215 will be interrupted for up to 14 days. While ASP2215 may be interrupted temporarily based on value on ECG tracing printout, the central reading should be used for final treatment decisions. Cardiology consult will be obtained as medically indicated. If QTcF resolves to ≤ 480 ms (grade 1 or less) by central reading within 14 days, the subject may resume dosing at the reduced dose.
- f. Urinalysis only required at screening. Uric acid will be tested on days 1, 4, 8 and 15 in cycle 1. Additional laboratory tests should be performed according to institutional standard of care.
- g. Subjects may be screened and randomized from local labs only. However, samples must also be submitted for central read. Labs and/or ECG can be repeated during screening period.
- h. MUGA scans or ECHO (per standard of care) are to be performed at screening for subjects with history of congestive heart failure New York Heart Association Class 3 or 4 (unless MUGA scans or ECHO performed either within 1 month prior revealed left ventricular ejection fraction ≥ 45%).

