6.1.3.3 Response Definition

Response to treatment will be defined per modified Cheson criteria [2003] as outlined below.

Response will be derived using myeloblast counts from centrally evaluated bone marrow aspirate if it's adequate. In case of non-adequacy, myeloblast counts from centrally evaluated bone marrow biopsy will be used. If neither central bone marrow aspirate nor biopsy is available, myeloblast counts will be imputed with locally evaluated bone marrow aspirate, if not available, locally evaluated bone marrow biopsy assessments. Centrally evaluated hematology results including ANC, platelet count and blast count in peripheral blood will be used in response derivation. Missing central hematology results will be imputed with local hematology results as collected on the eCRF.

Response will be derived for all post-baseline visits on or after 21 days from first dosing date.

• Complete Remission (CR)

For subjects to be classified as being in CR at a post-baseline visit, they must have bone marrow regenerating normal hematopoietic cells and achieve a morphologic leukemia-free state and must have an absolute neutrophil count (ANC) $\geq 1 \times 10^9$ /L and platelet count $\geq 100 \times 10^9$ /L, and normal marrow differential with < 5% blasts, and they will be red blood cell (RBC) and platelet transfusion independent (defined as 1 weeks without RBC transfusion and 1 week without platelet transfusion). There must be no presence of Auer rods. There should be no evidence of extramedullary leukemia. The blast counts in peripheral blood must be $\leq 2\%$.

• Complete Remission with Incomplete Platelet Recovery (CRp)

For subjects to be classified as being in CRp at a post-baseline visit, they must achieve CR except for incomplete platelet recovery ($< 100 \times 10^9/L$).

• Complete Remission with Incomplete Hematological Recovery (CRi)

For subjects to be classified as being in CRi at a post-baseline visit, they must fulfill all the criteria for CR except for incomplete hematological recovery with residual neutropenia $< 1 \times 10^9 / L$ with or without complete platelet recovery. RBC and platelet transfusion independence is not required.

• Composite Complete Remission (CRc)

For subjects to be classified as being in CRc at a post-baseline visit, they must either achieve CR, CRp or CRi at the visit.

• Complete Remission with Partial Hematologic Recovery (CRh)

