At a post baseline visit, subjects will be classified as CRh if they have marrow blasts < 5%, partial hematologic recovery ANC >= 0.5×109 /L and platelets >= 50×109 /L, no evidence of extramedullary leukemia and cannot be classified as CR. The blast counts in peripheral blood must be $\leq 2\%$

• Partial Remission (PR)

For subjects to be classified as being in PR at a post-baseline visit, they must have bone marrow regenerating normal hematopoietic cells with evidence of peripheral recovery with no (or only a few regenerating) circulating blasts and with a decrease of at least 50% in the percentage of blasts in the bone marrow aspirate with the total marrow blasts between 5% and 25%. A value of less or equal than 5% blasts is also considered a PR if Auer rods are present. There should be no evidence of extramedullary leukemia.

• Not Evaluable (NE)/No Response (NR)

In the situation where no bone marrow assessments are performed or myeloblast value is missing, blast value from peripheral blood is missing or <=2%, and extramedullary leukemia is missing or not present, the response will be classified as not evaluable (NE). In any case response cannot be categorized as CR, CRp, CRi, PR or NE, it will be categorized as NR

Relapse

Relapse after CR, CRh, CRp or CRi is defined as a reappearance of leukemic blasts in the peripheral blood (> 2%) or $\ge 5\%$ blasts in the bone marrow aspirate not attributable to any other cause or reappearance or new appearance of extramedullary leukemia.

Relapse after PR is similarly defined with reappearance of significant numbers of peripheral blasts and an increase in the percentage of blasts in the bone marrow aspirate to > 25% not attributable to any other cause or reappearance or new appearance of extramedullary leukemia.

Best Response

Best response is defined as the best measured response to treatment for all visits (in the order of CR, CRp, CRi, PR, NR and NE) post-baseline. Subjects who achieve the best responses of CR, CRp, CRi, or PR will be classified as responders. Subjects who do not achieve at least a best response of PR will be classified as non-responders.

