		Updated Section 7 Statistical	Due to new CRF pages
		Methodology:	added
		Added analysis method for	
		clinical/Diagnostic procedure and	
		subsequent AML therapy	
		Updated Section 7 Statistical	Updated due to Protocol
		Methodology:	amendment 7 dated 8-
		Removed treatment compliance	Aug-2016
		analysis due to unreliable drug	
		accountability data	
		Updated Section 7 Statistical	Updated due to protocol
		Methodology:	amendment 8 dated 20-
		 Added a table to summarize 	Sep-2017
		the timing, sample size and	
		decision guidance for all	
		planned analyses;	
		 Changed the primary 	
		analysis method from Cox	
		proportional hazard model to	
		stratified log-rank test;	

Version	Date	Changes	Comment/rationale for	
			change	
		 Added several new sensitivity analyses for OS, EFS and CR rate; Changed the hypothesis from 2-sided to 1-sided for OS, EFS and CR rate Added the entire section to describe the CR/CRh rate analysis method; Added the analysis for duration of CR/CRh and time to CR/CRh; Removed the analysis of AE, SAE during the on-study HSCT period; Added the grade 3 and 4 summary for selected lab test parameters; Added the CR/CRh endpoint for subgroup analysis; Modified the category for central FLT3 mutation type and region for subgroup variables; Modified the interim analysis section; Modified the blinding section 	change	
		Updated Section 7 Statistical Methodology: Added how to handle partial date in subsequent AML therapy; Modified the pooling strata section Updated Section 7 Statistical	For clarification purpose It is redundant	
		Methodology: Removed the visit window table	it is reduited.	
3.0 (Amendment 2)	27-SEP-2018	Updated Section 5.4.1 Reasons for Exclusion From PPS to add two criteria: - Neither central FLT3 mutation nor local FLT3 mutation with rapidly progressing disease at baseline -No active relapse at baseline	To clarify the detailed Reasons for Exclusion From PPS criteria.	
		Updated Section 5.7 Pharmacokinetics Analysis Set (PKAS) to clarify that the PKAS is for ASP2215 patients only and both	To clarify the detailed PKAS criteria.	

Version	Version Date Changes		Comment/rationale for
			change
		dosing date/time and sampling	
		date/time must be available.	
		Updated Section 6.1.3.1 and 7.4.3.1	Clarify the EFS definitions
		to clarify the definition of EFS and	regarding to handling of
		add additional sensitivity analysis:	deaths (for EFS event of

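### CR, CRh and CRc are defined by post-baseline status alone, so a randomized subject with no active leukemia at baseline can count as a responder in the single-arm CR/CRh rate

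*SAP*

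**What the plan says.** The second primary objective (SAP Section 3.1.1) is the CR/CRh rate in subjects who are refractory to, or have relapsed after, first-line therapy. Section 6.1.2 sets the rate thus: "number of subjects who achieve either CR or CRh (as defined in Section 6.1.3.3) at any of the post-baseline visit divided by the number of", with the analysis population as denominator.

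Section 6.1.3.3 supplies the response categories:

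- For CR, "they must have bone marrow regenerating normal hematopoietic cells and achieve a morphologic leukemia-free state", with further conditions on counts, blasts, transfusions, Auer rods and extramedullary disease. CRp and CRi are variants of this.
- For CRh, "At a post baseline visit, subjects will be classified as CRh if they have marrow blasts < 5" percent, with conditions on ANC, platelets, peripheral blasts and extramedullary leukemia.
- For CRc, "For subjects to be classified as being in CRc at a post-baseline visit, they must either achieve CR, CRp or CRi at the visit".
- PR alone refers to a change, "with a decrease of at least 50% in the percentage of blasts in the bone marrow aspirate".

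Response is derived at visits at least 21 days after first dose. On the source of the data, "Response will be derived using myeloblast counts from centrally evaluated bone marrow aspirate if it's adequate", with stated fallbacks.

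Sections 7.4.2 and 7.10 compare the lower limit of the two-sided 95% exact interval in about 141 ASP2215 subjects with 12%. Above 12% the result is Favorable. Section 7.10 says the sponsor may use the result for a conditional-approval submission.

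The revision history (Section 8, version 3.0) records a reason for exclusion from the PPS: "No active relapse at baseline".

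**The concern.** Remission is meant to describe a change from leukemia to no leukemia. As written, the four remission categories and CRh test only the end state. A subject whose marrow already has fewer than 5% blasts at baseline, with adequate blood counts, can meet CR or CRh at the first evaluable visit without any treatment effect.

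The first-interim evaluation has no control arm, so each such subject adds directly to a rate that is compared with a fixed benchmark. The same derivation feeds the ITT comparison of CR (Section 7.4.3.1), the CRc rate, the final CR/CRh summaries (Section 7.4.6) and the responder-only summaries of LFS, duration and time to remission.

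**Working it through.** **1. Is there a baseline-disease condition anywhere?** Sections 6.1.2 and 6.1.3.3 contain none for CR, CRp, CRi, CRc or CRh. Non-responder imputation in Section 7.11.1 deals with missing data. The first-interim sensitivity analyses in Section 7.4.2 are: mRAS, at least one dose, at least one post-baseline marrow, response by cycle 4, and response before HSCT. As described, none removes subjects without baseline leukemia. The PPS is listed for OS, EFS, CR rate and final CR/CRh (Sections 7.4.1, 7.4.3.1 and 7.4.6), but not for the first interim.

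**2. Reproduce the plan's figures.** Inputs from Sections 4 and 7.10: n = 141, benchmark 12%, assumed rate 21%, two-sided 95% exact interval. The lower limit for x responders is the 2.5% quantile of Beta(x, 141 − x + 1).

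| x of 141 | Lower limit | Label |
|---|---|---|
| 24 | 11.22% | Unfavorable |
| 25 | 11.82% | Unfavorable |
| 26 | 12.41% | Favorable |

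These match the table in Section 4, and the cut-off is 26. Power is P(Bin(141, 0.21) ≥ 26) = 0.8007, against the stated 80%. The chance of Favorable at a true 12% is P(Bin(141, 0.12) ≥ 26) = 0.0170.

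**3. Add k subjects without baseline leukemia.** The SAP gives no value for k, so 0 to 3 is an assumed range. Treating each as certain to count, which is an upper bound, the chance of Favorable is P(Bin(141 − k, p) ≥ 26 − k).

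| k | p = 12% | p = 21% |
|---|---|---|
| 0 | 1.7% | 80% |
| 1 | 2.7% | 85% |
| 2 | 4.3% | 88% |
| 3 | 6.5% | 92% |

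The interval's nominal error is 2.5% per side.

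**4. When does the label change?** With k = 1, only if the genuine count is 25 (25 + 1 = 26). With k = 2, only if it is 24 or 25. As a guide, a Bin(141, p) count is 24 or 25 with probability 3.2% at p = 12% and 9.8% at p = 21%.

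**5. Effect of a baseline rule.** Counting the subjects as non-responders gives back 25/141 (11.82%) or 24/141 (11.22%), both Unfavorable. Dropping them from numerator and denominator gives 25/140 (11.90%) or 24/139 (11.39%), also Unfavorable.

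**The case against.** The strongest reply is that active disease at entry is an eligibility matter. The trial is for relapsed or refractory AML, a subject without it may be a PD1 deviation tabulated under Section 7.2.2, and the words achieve and remission imply a transition. That limits how many such subjects there can be. It does not remove them: ITT keeps everyone randomized, and no derivation rule applies the transition reading.

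Several qualifications stand:

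- **Counting is not automatic.** CR also needs transfusion independence, no Auer rods and no extramedullary leukemia, and every criterion must hold on or after day 21. The table in step 3 is therefore an upper bound.
- **RAS and mRAS are not defined in the current text.** Section 7.4.2 describes the RAS by randomization and 112 days of follow-up, which suggests no exclusion, but one cannot be fully ruled out.
- **The PPS entry dates from version 3.0** (27 September 2018), whose revision notes already refer to knowledge from the first interim. It shows that such subjects were recognized by then, not that they were foreseen for that interim.
- **The interim evaluation is not a formal test** and does not affect study conduct (Section 7.10).

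A reader might also infer a route by which subjects enter on a local marrow read and prove leukemia-free centrally, because the schedule footnote says "Subjects may be screened and randomized from local labs only". The documents do not support this. That footnote is attached to the ECG and clinical laboratory rows. The marrow row carries a different footnote, which says nothing about randomizing on local reads.

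Nor can a bias in favor of ASP2215 be inferred for the randomized CR comparison, since such subjects may fall in either arm.

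**Conclusion.** The concern holds as a gap in the response definition. A subject without active leukemia at baseline who meets the criteria on or after day 21 counts as a responder, and the first interim has no listed analysis that visibly shows the effect.

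The size depends on an unknown number of subjects. On the assumed range and upper bound above, two such subjects raise the chance of Favorable at a true 12% from 1.7% to 4.3%, past the nominal 2.5% per side. At 21% they raise it from 80% to 88%.

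A reader might infer that one or two such subjects would generally turn the result. They do so only next to the cut-off, at a genuine count of 25 or 24. Nothing in the SAP shows that the reported result was affected.

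**What to change.** In Sections 6.1.2, 6.1.3.1 and 6.1.3.3, add one rule. A subject whose baseline assessment shows no leukemia (marrow blasts <5%, peripheral blasts ≤2%, no extramedullary leukemia, read by the same central-then-local hierarchy as response) stays in the denominator and counts as a non-responder for CR, CRh, CR/CRh and CRc. Report the number of such subjects by arm, and give the current definition as a sensitivity analysis.

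State two consequences explicitly:

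- The relabeling applies to the response rates only and does not by itself create an EFS treatment-failure event at randomization.
- These subjects are left out of the responder-only summaries of LFS, duration and time to remission.

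The cost is one derivation rule plus these two statements. The screening marrow is already required, so no new data are needed. Observed response rates may fall slightly. Version 4.0 plans no further efficacy analysis, since efficacy was reported at the 17 September 2018 cutoff. Applying the rule now would therefore mean a supplementary re-derivation on existing data.

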6.1.3 Secondary Efficacy Endpoints

6.1.3.1 Key Secondary Efficacy Endpoints

• Event-free survival (EFS)

EFS is defined as the time from the date of randomization until the date of documented relapse (excluding relapse after PR), treatment failure or death from any cause within 30 days after the last dose of study drug, whichever occurs first [earliest of (relapse date, treatment failure date, death date) – randomization date + 1].

If a subject experiences relapse or death within 30 days after the last dose of study drug, the subject is defined as having EFS event related to either "relapse" or "death", and the event date is the date of relapse or death.

If a subject discontinues the treatment and fails to achieve any of the response of CR, CRp or CRi during the treatment period (subject with best response of PR or NR), the subject is defined as having EFS event related to treatment failure, and the event date is the randomization date. Subjects that discontinue the treatment with post-treatment disease assessment and best response of NE will be censored.

For a subject who is not known to have relapsed or treatment failure or death, EFS is censored at the date of last relapse-free disease assessment (last relapse-free disease assessment date – randomization date +1). Subject is not censored at HSCT. For subjects who are censored, last relapse-free disease assessment date refers to the subject's last disease assessment date. Subject without post-treatment disease assessment or without study treatment will be censored at randomization date.

EFS will be tested at the second interim and final analysis only when OS is rejected. No formal evaluation on EFS will be conducted at the first interim. During second interim analysis and final analysis, only death, relapse, treatment failure occurring on or prior to the cutoff date are counted as EFS events. Subjects without these events before cutoff date will be censored at the last relapse-free disease assessment date post-baseline on or before the cutoff date

Disease assessment date refers to the date of central bone marrow aspiration or biopsy assessment. In the event that central bone marrow assessment is not performed or bone marrow is not adequate, local bone marrow assessment date will be used. If no aspirate or biopsy is available and subject is evaluated based on blast count from peripheral blood the date the peripheral blood sample is drawn will be used. If none of the above is available and subject is evaluated based on the presence of extramedullary leukemia, the assessment date of extramedullary leukemia will be used.

The following sensitivity analyses for EFS will be conducted:

- EFS will be defined similarly as the above primary analysis, however the date of the first new anti-leukemia therapy or the last treatment evaluation (when new anti-leukemia therapy date is not available), will be used as the event date of treatment failure.

- Sensitivity analysis of EFS will be performed to evaluate the impact of loss to follow-up on EFS. EFS will be defined similarly as the above primary analysis, however, subjects who discontinue the treatment due to "Lost to follow up" will also be considered as an EFS event (See Section 7.4.3.1 for details of "Lost to follow up" event), and the event date is withdrawal date or last evaluation date as collected on end of treatment, end of 30-day follow up, and end of long-term follow up CRF page whichever occurs first.
- EFS will be defined similarly as the above primary analysis with the following differences:
 - Subjects who discontinue the treatment and achieve best response of NR only will be defined as treatment failure and the event date is the randomization date
 - Subjects who discontinue the treatment and achieve best response of CR, CRp, CRi or PR and experience relapse will be defined as relapse and the event date is the date of first NR after CR, CRp, CRi or PR.
- EFS will be defined similarly as the above primary analysis, however, subjects who discontinue the treatment with post-treatment disease assessment and achieve best response of PR, NR or NE will be defined as treatment failure and the event date is the randomization date.
- Complete remission (CR) rate

CR rate is defined as the number of subjects who achieve the best response of CR divided by the number of subjects in the analysis population. As a sensitivity analysis, CR rate prior to HSCT will be defined as the number of subjects who achieve CR prior to HSCT divided by the number of subjects in the analysis population.

CR rate will be tested at the second interim and final analysis only when both OS and EFS are rejected. No formal evaluation on CR rate will be conducted at the first interim.

